4.8.3 Vital Signs

Vital signs data will be summarized by visit (and timepoint if applicable). Descriptive statistics will be provided for the observed value and the change from baseline values. If a subject has multiple results on the vital signs at a particular visit, the last non-missing value will be used for the summary.

All vital signs data will be presented for each subject in a data listing.

4.8.3.1 Orthostatic Hypotension

The number (%) of subjects experiencing orthostatic hypotension will be summarized by visit and time point. Orthostatic hypotension will be defined as a decrease in systolic blood pressure (SBP) of ≥ 20 mmHg from seated or supine to standing or in diastolic blood pressure (DBP) of ≥ 10 mmHg from seated or supine to standing.

4.8.3.2 Pulse

Descriptive statistics will be provided for the observed value and the change from pre-dose values by visit. The number (%) of subjects experiencing pulse increase from pre-dose and the occurrence per subject will be summarized with various threshold values (ranging from >5 bpm to >40 bpm).

4.8.4 Electrocardiogram

Descriptive statistics will be provided to summarize ECG parameters and changes from baseline by visit and time point. The ECG parameters include heart rate (bpm), RR interval (msec), PR interval (msec), QRS duration (msec), QT interval (msec), and QTcF (Fridericia) (msec). In the event of repeat or unscheduled assessments for a given time point, the last non-missing value for the time point will be used in the tabulations.

Descriptive statistics will be provided for the observed value and the change from pre-dose values by visit. The number (%) of subjects experiencing heart rate increase from pre-dose and the occurrence per subject will be summarized with various threshold values (ranging from >5 bpm to >40 bpm).

5 CHANGES FROM THE PROTOCOL-SPECIFIED ANALYSES

The Bone Metabolism Population is not defined in the protocol and has been added in the SAP. It is defined as subjects in the Safety population who have baseline and at least one post-baseline s-PINP.

All other statements in this SAP are enhancements to the statistical considerations described in the protocol.

Signature Page for RAD-CLIN-001231 v1.0

Approval	
	20-Jun-2019 13:59:04 GMT+0000
Approval	
	20-Jun-2019 14:02:55 GMT+0000
Approval	
	20-Jun-2019 14:10:51 GMT+0000
Approval	
	20-Jun-2019 14:30:15 GMT+0000
Approval	
	20-Jun-2019 14:30:28 GMT+0000
Approval	
	20-Jun-2019 14:49:49 GMT+0000
Approval	
	20-Jun-2019 14:57:59 GMT+0000
Approval	
	20-Jun-2019 16:41:01 GMT+0000

Signature Page for RAD-CLIN-001231 v1.0

Signature Page for RAD-CLIN-001231 v1.0

Approval

 20-Jun-2019 18:15:14 GMT+0000

Signature Page for RAD-CLIN-001231 v1.0

Strategic Consulting

PHARMACOMETRIC ANALYSIS PLAN

A PROSPECTIVE, SINGLE ARM STUDY TO EVALUATE THE PK, PD AND USABILITY OF ABALOPARATIDE-sMTS IN POSTMENOPAUSAL WOMEN WITH LOW BONE MINERAL DENSITY

Final

Date: 27-May-2019

Sponsor Protocol No.: BA058-05-022 (Version 1.0)

Investigational Product: Abaloparatide-sMTS

CSC Reference No.: RADI-NCA-ABALOPARATIDE-985

Radius Health, Inc. (Radius)

CONFIDENTIALITY STATEMENT

[figure not shown]
Information contained in this document is proprietary to Radius Health, Inc. The information is provided to you in confidence to enable you to perform the work, which is requested under an agreed upon and signed confidentiality statement. Do not give this document or any copy of it or reveal any proprietary information contained in it to any third party (other than those in your organization who are assisting you in this work and are bound by the confidentiality statement) without the prior written permission of an authorized representative of Radius Health, Inc.

SIGNATURE PAGE

Protocol No.: BA058-05-022

Study Title: A Prospective, Single Arm Study to Evaluate the PK, PD and Usability of Abaloparatide-sMTS in Postmenopausal Women with Low Bone Mineral Density

CSC Reference No.: RADI-NCA-ABALOPARATIDE-985

27-may- 2019

Date

Certara Strategic Consulting

4 LIST OF ABBREVIATIONS

Term	Definition
%AUC _{extrap}	Extrapolated portion of AUC _{0-inf} from t _{last} to infinity
ADaM	Analysis Data Model
ADPC	Analysis dataset containing PK concentrations
ADPP	Analysis dataset containing PK parameters
ADRG	Analysis Data Reviewer's Guide
AUC	Area under the curve
BLQ	Below the limit of quantification
C _{max}	Maximal plasma concentration
CRF	Case report form
CSC	Certara Strategic Consulting
CV%	Coefficient of variation
DTS	Data transfer specification document
EOT	End of treatment
FTP	Secured file transfer protocol
IFU	Instruction for use
LLOQ	Lower limit of quantification
n	Sample size
Max	Maximum
Min	Minimum
NCA	Noncompartmental analysis
PAP	Pharmacometric Analysis Plan
PD	Pharmacodynamics
PK	Pharmacokinetic(s)
QA	Quality Assurance
QC	Quality Control
SD	Standard deviation
SDRG	Submission Data Reviewer's Guide
SDTM	Study Data Tabulation Model
sMTS	Solid microstructure transdermal system
SOP	Standard operating procedure
t _{max}	Time to maximal concentration

5 SCOPE

This Pharmacometric Analysis Plan (PAP) was created using the study protocol BA058-05-022, Version 1.0, dated 18 March 2019. Any further changes to the protocol may require updates to the current analysis plan.

This analysis plan addresses the pharmacokinetic (PK) analysis of abaloparatide-solid Microstructured Transdermal System (sMTS) in plasma in postmenopausal women with low bone mineral density. The intended methods of data analysis and reporting are included in the current analysis plan. This document provides guidance to the extent, scope, and method of analysis. However, due to uncertainty of the nature of the data *a priori*, deviations from this plan may be necessary and will be documented.

The final methods of analysis and results will be reported in the PK Report. Deviations from this plan will be noted.

6 ANALYSIS PLAN OBJECTIVES

[figure not shown]
- To characterize the PK profile of abaloparatide-sMTS in postmenopausal women with low bone mineral density following daily self-administrations of 300 µg abaloparatide-sMTS for 5 minutes over a period of 29 days.

7 STUDY DESIGN

7.1 General Study Design

This is an open-label study to evaluate the usability of the abaloparatide-sMTS by subjects with low bone mineral density. The study will consist of a Screening Period (up to 2 months), a Pre-Treatment Period (1 week), a Treatment Period (29 days), and a Follow-Up Period (7 days) after the last dose of study medication. During the Treatment Period, subjects will have clinic visits for study-related protocol procedures at Day 1 (Visit 3), Day 15 (Visit 4) and on Day 29 (Visit 5/End of Treatment (EOT)). The Treatment Period of the study will be considered complete when the last subject completes the last clinic visit. The study design is presented in **Figure 7.1**.

Figure 7.1 Study Design

Study Visits

7.2 Schedule of Drug Administration

The first self-administration is to occur at the study site on Day 1, under observation.

Subjects will be trained by study personnel to self-administer study medication with the abaloparatide-sMTS patch and applicator. Subjects will self-administer a single daily dose of 300 µg of abaloparatide-sMTS to the thigh for 5 minutes during the treatment period, following the Instructions for Use (IFU).

The subject is to remain under observation for a minimum of 60 minutes after the initial abaloparatide-sMTS removal on Day 1.

On the days when blood sampling is required after study medication administration, the subject is to remain at the vicinity of the clinic for the blood collections scheduled up to 4 hours post-administration of the study medication.

7.3 Number of Subjects

Approximately 22 subjects will be enrolled and treated to ensure a minimum of 18 subjects complete the 29-day treatment and study procedures.

7.4 Pharmacokinetic Assessments

Blood samples for measurement of plasma concentrations of abaloparatide will be taken at Day 1, Day 15 and on Day 29. The pharmacokinetic measurements will be assessed predose and at 10 minutes, 20 minutes, 30 minutes, 1 hour, 1.5 hours, 2 hours, 3 hours and 4 hours after abaloparatide-sMTS application.

8 ANALYSIS SETS

8.1 Pharmacokinetic Analysis Population

The Pharmacokinetic Analysis Population will include all subjects who received at least one dose of study medication and have sufficient evaluable plasma concentrations to reliably estimate one or more PK parameters.

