## 2. STUDY OBJECTIVES AND ENDPOINTS

## 2.1. Objective

The primary objective of this study is to evaluate the ability of subjects to self-administer 300  $\mu g$  abaloparatide-sMTS over a period of 29 days based on pharmacokinetic (PK) and pharmacodynamic (PD) markers.

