## **5.3.** Study Medication Administration

Subjects will be encouraged to drink 8 ounces of water 1 to 2 hours prior to dosing.

Prior to the administration of study drug, the application site will be prepped and cleaned with an alcohol wipe, allowed to air dry, and then examined in order to assure that the area is not compromised. Each application site will be graded according to a 4-point scale by the investigator to assess signs of local skin reactions (at clinic visits; Section 6.6.2.1) and by the subject to assess symptoms of local skin reactions (each day during the treatment period; Section 6.6.2.2), prior to abaloparatide-sMTS application, immediately after removal of abaloparatide-sMTS, and at 1 hour after abaloparatide-sMTS application. For any severe local skin reactions, evaluations by the

subject will continue at 24 hour intervals until the reaction has stabilized or resolved (see Section 6.6.2.2).

Before initial use of abaloparatide-sMTS, the subject will be trained on the Instructions for Use and will demonstrate their ability to self-administer the abaloparatide-sMTS with the Investigator present. During subsequent applications, the subject will follow the Instructions for Use. It is important to note that if any component is damaged, the subject is to be instructed to replace the abaloparatide-sMTS patch with a new one and place the damaged patch in a container that was provided and to bring this together with the other used and unused abaloparatide-sMTS at the next clinic visit. Please refer to the pharmacy manual for additional details.

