## 8.3. Analysis Datasets

## 8.3.1. Population for Analysis

The primary population for all safety analyses will be the Safety Population, which will be defined as all subjects who received at least 1 dose of study medication.

The primary population for PK analyses will be the Pharmacokinetic (PK) Analysis Population, which will include all subjects in the Safety Population who have sufficient evaluable plasma concentrations to reliably estimate 1 or more PK parameters.

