1.1 Study Objectives

The primary objective of this study, as stated in Section 2 of the protocol, is to evaluate the ability of subjects to self-administer 300 µg abaloparatide-sMTS over a period of 29 days based on pharmacokinetic (PK) and pharmacodynamic (PD) markers.

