1.2.5 Study Endpoints

1.2.5.1 Primary Endpoint

The primary endpoint is the systemic exposure of the drug at Day 1, Day 15 and Day 29. Details for the analysis of the primary endpoint are provided in the Pharmacometric Analysis Plan (PAP).

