9.1 Study Variables

9.1.1 Concentration Data

Concentration values of plasma abaloparatide-sMTS that are reported as below the limit of quantitation (BLQ) will be set to zero for PK parameter calculation and concentration summary statistics.

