9.2.3 Statistical Analysis

Comparisons between the abaloparatide PK parameter values on Day 15 and on Day 29 vs Day 1 will be conducted. Variable identifying the day (e.g., PKDAY or VISIT) will be used as fixed effect.

The log transformed AUC0-t, AUC0-inf, and Cmax will be compared among the visits following the methodology of the longitudinal data analysis using a repeated measures model. SAS® Proc MIXED will be used to account for the possibility of having the unbalanced data. Model will have no random effects, however, since the repeated observations for the same subject made on several days will be used in the model, several forms of variance covariance matrices will be explored, e.g., compound symmetry (CS), the first- or nth-order autoregressive covariance matrices, [AR(1) and TOEP respectively], and unstructured (UN) form. The one that produces the minimal corrected Akaike information criterion (AICC) will be used in the final model. Point estimates and 90% CIs for treatment differences on the log scale, obtained from the model, will be exponentiated to obtain estimates on original scale.

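### The log-scale comparison of Day 15 and Day 29 exposure with Day 1 omits any clinic application with no quantifiable drug, so it cannot show outright delivery failure

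*SAP*

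**What the plan says.** Protocol section 2.1 opens: "The primary objective of this study is to evaluate the ability of subjects to self-administer" the 300 µg patch over 29 days, judged on PK and PD markers. SAP section 1.1 repeats this. SAP section 1.2.5.1 then states: "The primary endpoint is the systemic exposure of the drug at Day 1, Day 15 and Day 29".

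The PAP, bound with the SAP, makes that endpoint operational:

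- **Population (PAP 8.1).** Subjects with at least one dose who "have sufficient evaluable plasma concentrations to reliably estimate one or more PK parameters". Protocol section 8.3.1 has the same rule: "who have sufficient evaluable plasma concentrations to reliably estimate 1 or more PK parameters". Both define the population by subject, not by visit, and neither defines evaluable.
- **BLQ values (PAP 9.1.1).** These "will be set to zero for PK parameter calculation and concentration summary statistics".
- **Parameters (PAP 9.1.2, Table 1).** AUC0-t runs to the last quantifiable concentration. AUC0-inf also needs a terminal slope from at least three measurable points after tmax.
- **Comparison (PAP 9.2.3).** "The log transformed AUC0-t, AUC0-inf, and Cmax will be compared among the visits" in a repeated-measures model fitted with PROC MIXED. Estimates and 90% CIs are exponentiated to give ratios to Day 1. There is no rule for a parameter equal to zero.

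**The concern.** An application that puts no measurable drug into the circulation is the clearest PK evidence that self-administration failed on that occasion. Exposure is the primary endpoint because it is meant to reveal such failures. The only between-visit comparison planned for that endpoint is on the log scale, where a zero has no value, so the visit is treated as missing. This follows from the scale alone and needs no decision to exclude anything.

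The Day 15 and Day 29 ratios could therefore sit near 1 and be read as maintained ability to self-administer, while some subjects received nothing measurable at those visits. The by-visit geometric means in the planned in-text tables carry the same condition.

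**Working it through.** **The plan's own figures.** The only planned number is about 22 subjects enrolled for at least 18 completers, an implied attrition of 1 − 18/22 = 18.2%. There is no power calculation to reproduce. The documents give no CV and no rate of delivery failure, so the failure numbers, failure rates and CVs below are assumptions.

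**Step 1: follow one all-BLQ profile through the rules.**

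- All concentrations become 0 (PAP 9.1.1), so Cmax = 0.
- There is no last quantifiable time, so AUC0-t has no endpoint under Table 1. Whether software returns zero or missing makes no difference on the log scale.
- There is no terminal slope, so there is no AUC0-inf.
- ln(0) is undefined, so the visit supplies no value of any compared parameter to PROC MIXED. The subject's other visits stay in. The geometric mean for that visit is likewise taken without her.

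**Step 2: direction and size.** Take 20 subjects with exposure 1 at every working application.

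- Two failures on Day 29: the model ratio is about 1.00. Mean exposure over all dosed is (18 × 1 + 2 × 0)/20 = 0.90, against 1.00 on Day 1. The ratio is too high.
- Two failures on Day 1 and none on Day 29: the model ratio is again about 1.00. The mean ratio is 1.00/(18/20) = 20/18 = 1.11. The ratio is too low.

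**Step 3: simulation at n = 18.** The true ratio is 1 for working doses, between- and within-subject CVs are both 30%, and k Day 29 profiles are all BLQ. The log-scale analysis used paired differences as a simple stand-in for the mixed model.

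| k of 18 | Log-scale ratio, zeros lost (average 90% CI) | Arithmetic mean ratio, zeros kept |
|---|---|---|
| 0 | 1.00 (0.85–1.18) | 1.00 |
| 1 | 1.00 (0.84–1.19) | 0.94 |
| 2 | 1.00 (0.84–1.20) | 0.89 |
| 4 | 1.00 (0.82–1.21) | 0.78 |

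The last column follows (n − k)/n. With CVs of 50% the log-scale ratio again stays at about 1.00 and the intervals are wider.

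**Step 4: does the subject leave the PK population?** She does so only if no visit yields an estimable parameter. If each clinic dose fails independently with probability p, all three fail with probability p³. For p = 5%, 10% and 20%, the expected number among 22 subjects is 22p³ = 0.003, 0.02 and 0.18. At least one of a subject's three visits fails with probability 1 − (1 − p)³ = 14%, 27% and 49%. The effect is on visits and hardly at all on subjects.

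**Step 5: could it arise?** With 22 × 3 = 66 profiles, the chance of at least one all-BLQ profile is 1 − (1 − p)^66, which is 49%, 74% and 97% for p = 1%, 2% and 5%.

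**The case against.** The best reply is that failures are visible elsewhere. BLQ zeros stay in the concentration means and medians (PAP 9.1.1 and 9.2.1). PK parameters also get arithmetic summaries (PAP 9.2.2). The table shells print N for each parameter and day, and individual concentrations are tabulated. Released dose from the same clinic applications is summarised by visit, with negative values counted as zero (SAP 4.7.7). Diary success, adhesion and compliance are also planned. The study is hypothesis-generating, has no formal tests, and judges its objective on PD as well as PK. All this stands, and it limits the consequence. It does not correct the visit comparison: a reduced N gives no reason, and no planned PK output counts applications without measurable drug over all those dosed.

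A reader might also infer four stronger points that the documents do not support.

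- **That a failed dose leaves the PK population.** The definition is by subject, and nothing states that all-BLQ profiles are excluded from it.
- **That exposure is judged only among successful applications.** Partial deliveries with measurable drug remain unless removed on review, and zeros remain in the concentration summaries.
- **That the bias always favours the patch.** Day 1 is the reference, and Step 2 shows that failures there act the other way.
- **That a woman who cannot work the applicator at training appears in no denominator.** Protocol section 5.3 says the subject "will demonstrate their ability to self-administer the abaloparatide-sMTS with the Investigator present", but it sets no pass/fail condition for dosing. Protocol section 6.2.7.1 lists training and then observed self-administration. The disposition summary (SAP 4.1) already reports reasons for exclusion from the Safety Population.

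**Conclusion.** The point holds for the visit comparison and the geometric means. As written, both are conditional on measurable delivery, and no number of all-BLQ applications at Day 15 or 29 would in itself lower the ratio. In the illustration the gap is 1.00 against 0.90 for 2 failures of 20. In the simulation it reaches 1.00 against 0.78 for 4 of 18.

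The direction depends on when failures occur. Those on Day 15 or 29 leave the ratio too high, and those on Day 1 leave it too low. The mechanism follows from the PAP's text. The size rests wholly on assumed failure counts, and if no profile is all BLQ the effect is nil. Because no decision rule depends on the ratio, this is a worthwhile and cheap improvement, not a flaw that invalidates the study.

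**What to change.** In PAP sections 8.1 and 9.2.3:

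1. State that dosed and sampled subjects with all-BLQ profiles stay in the PK population, with Cmax = 0 and AUC0-t = 0 for the arithmetic mean, median and listings.
2. Report by visit the number and proportion of clinic self-applications with any quantifiable concentration. The denominator is all subjects dosed and sampled at that visit, and the result sits beside the geometric mean ratios.
3. Label the log-scale ratios as conditional on measurable delivery.

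Replacing zeros with a small constant so that they fit the log model is not a good substitute, because the answer then depends on the constant. With 1 zero in 18 replaced by a fraction f of typical exposure, the ratio is f^(1/18), which is 0.88, 0.85 or 0.77 for f = 10%, 5% or 1%.

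The cost is a few sentences and one small table from data already collected. The downside is that reported exposure may look slightly less favourable.

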9 METHODS

Study data tabulation model (SDTM) and analysis data model (ADaM) clinical datasets (subject identification, dosing times, blood sample collection times, dosing information, etc.) will be transferred from Radius to Certara Strategic Consulting (CSC) via a secured file transfer protocol (FTP), secure file sharing services or password-protected e-mail. Final data will be transferred after the final database lock. It is expected that all final SDTM and ADaM data transferred to Certara from Radius will be validated and quality controlled or quality assured before being sent to Certara. Inconsistencies in the data will be communicated to Radius and may result in a delay in the analysis timelines. For the ADaM datasets, Radius will provide a Specification Document in Excel format to Certara describing each variable in the datasets. For SDTM datasets, any study specific information will be provided to Certara from Radius.

All electronic files that are sent via e-mail to CSC will be addressed to the following CSC designate:

[REDACTED]
[REDACTED]
Certara Strategic Consulting
e-mail: [REDACTED]

Certara will provide to Radius one SDTM dataset containing PK parameters (PP), one analysis dataset containing PK concentration (ADPC) and one analysis dataset containing PK parameter (ADPP) as well as Submission Data Reviewer's Guide (SDRG) and Analysis Data Reviewer's Guide (ADRG) for creating define.xml. Datasets will contain data used for the analysis performed. A test transfer will be made to insure compliance with the data transfer specification document (DTS). Files will be transferred following acceptance of Radius of the results of the test transfer.

9.1 Study Variables

9.1.1 Concentration Data

Concentration values of plasma abaloparatide-sMTS that are reported as below the limit of quantitation (BLQ) will be set to zero for PK parameter calculation and concentration summary statistics.

9.1.2 Pharmacokinetic Parameters of Abaloparatide-sMTS in Plasma

All plasma PK parameter calculations will be performed using actual or nominal times (when actual time is not available) calculated relative to the time of study drug administration in hours. PK parameters will be determined using noncompartmental (NCA) methods¹ based on individual plasma concentration-time data for abaloparatide-sMTS (Table 1).

Table 1: Pharmacokinetic Parameters of Abaloparatide-sMTS in Plasma

Parameters	Description
AUC _{0-t}	Area under the plasma concentration-time curve from time zero to the time of the last quantifiable concentration (t_{last}) using the linear up-log down trapezoidal rule
AUC _{0-inf}	Area under the plasma concentration-time curve from time zero to infinity calculated using the formula $AUC_{0-t} + (C_{last} / \lambda_z)$, where C_{last} is the last quantifiable concentration and λ_z is the first-order terminal rate constant, calculated by log-linear regression analysis over the terminal log-linear segment of the plasma concentration-time curve. AUC _{0-inf} was calculated using the linear-up log down trapezoid rule.
C _{max}	Maximum observed plasma concentration
t _{max}	Time of maximum observed plasma concentration
t _{1/2}	Apparent terminal phase half-life, calculated as $\ln(2) / \lambda_z$
λ_z	Elimination rate constant

Assessments of λ_z will include the following key considerations:

- At least 3 time points (in which the first time point must be greater than t_{max}) with measurable plasma concentrations will be required for the calculation of λ_z .
- λ_z must be positive, and calculated from at least three data points in the terminal phase of the concentration-time profile.
- Points prior to t_{max} are not used.
- t_{max} is not included.
- $R^2_{adj} \geq 0.8$ for the log-linear regression analysis of λ_z .

No value for λ_z and other λ_z -related parameters (e.g., AUC_{0-inf} and t_{1/2}) will be reported for concentration profiles that do not exhibit an elimination phase in the concentration versus time profile (i.e., if $R^2_{adj} < 0.8$ for the log-linear regression analysis of λ_z).

For the assessment of λ_z , if the extrapolated portion of AUC_{0-inf} from t_{last} to infinity (%AUC_{extrap}) for a subject is greater than 20%, the λ_z -related PK parameters will be listed for that subject, and the λ_z and λ_z -related PK parameters will be excluded from descriptive statistics with a corresponding footnote to highlight that %AUC_{extrap} is greater than 20%.

If a dose of abaloparatide-sMTS is missed or if the patch did not adhere correctly to the skin, the complete corresponding concentration-time profile may be excluded from the PK analysis and/or summary statistics after review by CSC and Radius on a case-by-case basis.

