## 1.2. Study Rationale

The purpose of this study is to evaluate the ability of subjects to self-administer 300 µg abaloparatide-sMTS over a period of 29 days based on analyses of pharmacokinetic (PK) and pharmacodynamic (PD) markers. The systemic exposure will be compared to historical exposure after treatment with abaloparatide SC as well as results from BA058-05-015,

Cohort 7, where subjects were treated with the same product as a single dose by a trained healthcare professional.

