## 2.2. Primary Endpoint

The primary endpoint is the systemic exposure of the drug at Day 1, Day 15 and Day 29.

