#### 6.6.4. Assessment of Patch Adhesion

The patch is to be assessed by the subject for adhesion immediately prior to the removal of abaloparatide-sMTS at each day during the treatment period. Adhesion scores will be scored according to the following scoring system and recorded in the subject diary:

- $0 = \ge 90\%$  adhered (essentially no lift off the skin)
- $1 = \ge 75\%$  to < 90% adhered (some edges only lifting off the skin)
- $2 = \ge 50\%$  to < 75% adhered (less than half of the patch lifting off the skin)
- 3 = 0% to < 50% adhered but not detached (more than half of the patch lifting off skin without falling off)
- 4 = 0% adhered patch detached (patch completely off the skin)

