9.3.2 Time Deviation

If the actual time of blood collection post-dose deviates by >20% from the nominal time, those sample concentrations will be reported (flagged with code “/t”) and included in the PK analysis. They will be excluded from the summary statistics in concentration tables and mean figures.

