9.3.3 Incomplete Dosing Information

Missing dose dates and/or times may be imputed using nominal dosing times. The imputation strategy will be discussed with Radius. All pharmacokinetic samples associated to a missing dosing date and/or time that cannot be imputed will be excluded from the analysis.

Subjects with a documented patch adherence issue will be reviewed by CSC and Radius for inclusion/exclusion from the descriptive statistics on a case-by-case basis.

In the case where subjects were dosed with abaloparatide-sMTS but discontinued from the study (early termination), the concentration data will be reported in the concentration tables and included in all summary statistics and PK analysis if sufficient concentration data are available to usefully contribute to the PK analysis.

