9.3.5 Unexpected Data

After database lock, a visual inspection of concentration-time profiles will be performed to determine dataset integrity and potential outliers. Descriptive statistics of PK parameters may be calculated with and without subjects with potential outlier data. Subjects with potential outlier data will be reviewed by CSC and Radius for inclusion/exclusion from the descriptive statistics on a case-by-case basis.

Single-dose PK profiles (i.e., Day 1) with non-zero pre-dose concentration values will be included in the computation of PK parameters and descriptive statistics on PK parameters and concentrations if the value is not greater than 5% of C_{max} . PK profiles with non-zero pre-dose concentration values greater than 5% of C_{max} will be identified in the PK report and will be reviewed by CSC and Radius for inclusion/exclusion from the PK calculations and descriptive statistics on concentrations and PK parameters.

Multiple observations at the same actual time point will be averaged for the calculation of PK parameters.

Any plasma concentrations that cannot be uniquely and unequivocally attributed to a particular subject, dose, or day and/or time point based on case report form (CRF) records or other observed

data records in the study will be treated as incomplete data. Such data will be compiled, commented, and listed separately in the appendix of the report. Incomplete and/or non-compliant data, if any, will be excluded from analysis datasets; no analyses, summaries or graphs will be produced using these data.

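### Profiles from poorly adhering self-applied patches may be dropped case by case, with no cut-off, no timing rule and no guaranteed all-profiles result, so per-visit exposure can be biased upward

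*SAP*

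**What the plan says.** Protocol 2.1 sets the primary objective as the ability of subjects to self-administer the patch over 29 days, judged on PK and PD markers. Protocol 2.2 adds: "The primary endpoint is the systemic exposure of the drug at Day 1, Day 15 and Day 29". Protocol 1.2 gives the intended use of the result: "The systemic exposure will be compared to historical exposure after treatment with abaloparatide SC as well as results from BA058-05-015"; in the cohort cited from that study, a trained healthcare professional applied the same product as a single dose.

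Three PAP sections bear on exclusion:

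- **9.1.2** allows removal of a whole profile: "if the patch did not adhere correctly to the skin, the complete corresponding concentration-time profile may be excluded from the PK analysis". The same sentence extends to summary statistics, also covers missed doses, and leaves each case to review by the PK vendor and the sponsor.
- **9.3.3** returns to adhesion: "Subjects with a documented patch adherence issue will be reviewed by CSC and Radius for inclusion/exclusion from the descriptive statistics", again case by case.
- **9.3.5** provides for visual inspection after database lock: "Subjects with potential outlier data will be reviewed by CSC and Radius for inclusion/exclusion from the descriptive statistics". Parameter statistics with and without such subjects are optional.

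The between-visit model in PAP 9.2.3 uses log-scale parameters: "The log transformed AUC0-t, AUC0-inf, and Cmax will be compared among the visits". The PK Analysis Population (Protocol 8.3.1, SAP 2.1, PAP 8.1) has no adhesion condition.

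An adhesion measure already exists. Under Protocol 6.6.4, "The patch is to be assessed by the subject for adhesion immediately prior to the removal of abaloparatide-sMTS", on a score from 0 (at least 90% adhered) to 4 (detached), every treatment day. The PAP does not refer to it.

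**The concern.** In most PK studies a badly applied dose is a nuisance. Here the user's success in applying the patch is what exposure is meant to measure. Removing the profile when adhesion is poor takes out the failures that the primary endpoint should capture.

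Three matters are left open:

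1. **Trigger.** Incorrect adhesion is not defined.
2. **Scope.** Section 9.1.2 reaches the PK analysis and/or summaries and acts on a profile. Section 9.3.3 reaches descriptive statistics only and acts on subjects. It cannot be determined whether a poorly adhering profile enters the 9.2.3 model.
3. **Timing and fallback.** Final data go to the PK vendor after database lock (PAP 9). Nothing requires adhesion decisions before concentrations are seen, and no all-profiles summary or model estimate is guaranteed.

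At stake are the visit geometric means, their variability, the two visit ratios and the historical comparison, which would describe successful self-applications only.

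**Working it through.** **Own figures.** The plan gives no adhesion failure rate, exposure loss, variability or power calculation, so there is no figure of its own to reproduce. Approximately 22 subjects are to be enrolled so that at least 18 complete (PAP 7.3).

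**How the PAP treats other data problems.**

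| Problem | Trigger | Consequence |
|---|---|---|
| Late or early sample (9.3.2) | over 20% from nominal time | flagged, kept in PK analysis, left out of concentration summaries |
| Day 1 predose above zero (9.3.5) | over 5% of Cmax | reviewed for inclusion |
| Extrapolated AUC (9.1.2) | over 20% | λz-related parameters listed, left out of descriptive statistics |
| Poor adhesion (9.1.2, 9.3.3) | none | whole profile may go |

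The sampling-time rule begins "If the actual time of blood collection post-dose deviates by >20% from the nominal time". Numeric triggers were therefore set elsewhere; adhesion is the problem closest to the objective and has none.

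**Assumptions.** n profiles at a visit, k adhesion failures, each with exposure r relative to full adhesion. I take n = 20 (between 18 and 22), with n = 18 as a check; k from 1 to 4; r from 0.30 to 0.75; geometric CV 40% under full adhesion.

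**Visit geometric mean**, relative to full adhesion:

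- All profiles kept: exp(k·ln r / n). Failures dropped: 1.00.
- Inflation from dropping: exp(−k·ln r / n) − 1.

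**Geometric CV with all kept:** v = ln(1 + 0.40²) + [k(n − k) / (n(n − 1))]·(ln r)², and gCV = √(exp(v) − 1).

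For n = 20, k = 3, r = 0.30:

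- mean: exp(3 × (−1.204) / 20) = 0.835; inflation 1/0.835 − 1 = 20%
- v = 0.1484 + (51/380) × 1.4496 = 0.1484 + 0.1945 = 0.343; gCV = 64%

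| n = 20 | Mean, kept | Mean, dropped | Inflation | gCV, kept | gCV, dropped |
|---|---|---|---|---|---|
| 1 failure at 50% | 0.966 | 1.00 | 3.5% | 43% | 40% |
| 3 failures at 30% | 0.835 | 1.00 | 20% | 64% | 40% |
| 4 failures at 30% | 0.786 | 1.00 | 27% | 69% | 40% |

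Inflation of the geometric mean at n = 18:

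| Failures | r = 0.75 | r = 0.50 | r = 0.25 |
|---|---|---|---|
| 1 | 1.6% | 3.9% | 8.0% |
| 2 | 3.2% | 8.0% | 16.7% |
| 3 | 4.9% | 12.2% | 26.0% |

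Three failures at 30% with n = 18 give 0.818 kept, an inflation of 22%.

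**Day 29/Day 1 ratio**, all kept, n = 20, r = 0.30, true ratio 1 for well-adhered patches: exp((k29 − k1)·ln r / 20).

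- 3 failures on Day 29 only: 0.835
- 3 on Day 1 only: 1.20
- 3 on each day: 1.00

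Dropping the failures gives 1.00 in all three cases. The ratio can therefore move either way; only per-visit exposure has a fixed direction. These are simple geometric means and ignore the mixed model's use of a subject's other visits.

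**Zero exposure.** PAP 9.1.1 sets values below the quantification limit to zero. An application with every sample below that limit has no logarithm and cannot enter the 9.2.3 model, whatever the adhesion rule. No count of such applications is planned.

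**The case against.** **Exclusions would be traceable.** The PAP plans individual concentration and parameter listings, individual and spaghetti plots, and an appendix listing excluded subjects; deviations from the plan are to be noted in the PK report. With about 22 subjects, a reader could see much of what was removed. This stands, but none of it gives an all-profiles mean or model estimate.

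**Failures should be rare on PK days.** Profiles come only from clinic visits, where dosing is supervised (Protocol 5.6), and damaged components are replaced (Protocol 5.3). This lowers the likely number of failures, and the milder rows of the tables may be nearer the truth. It is no reason to leave the rule open.

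**The bias is conditional.** The exclusion is permitted, not required, and no document shows that a low score just before removing a five-minute patch means lower exposure. Correct: the direction rests on that premise.

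**Little turns on it.** This is a single-arm, hypothesis-generating study with no formal tests and no exposure limit to pass, and the historical comparison appears in Protocol 1.2 but not in the PAP's model. No pre-specified decision can flip. The visit means and 90% intervals are nevertheless the primary result.

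**Other data keep failures visible.** Adhesion, released dose and user errors are tabulated (SAP 4.7.6 to 4.7.8), and the PD analyses have no adhesion exclusion. That helps interpretation without restoring the exposure estimate.

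**The scope conflict may be loose drafting.** Section 9.3.3 can be read as a case within 9.1.2. Even so, entry to the mixed model stays undetermined.

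**All-BLQ profiles can be found in the shells.** They show values below the limit by subject and an N per parameter. True, so the requested count is a small addition.

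**Conclusion.** The concern holds. For applied patches that adhere poorly, the PAP gives no definition, no decision time and no guaranteed result on all profiles, in a study where application success is the primary question. If poor adhesion lowers delivery, using the rule must raise that visit's mean exposure. On the assumed values the inflation runs from 1.6% (one failure at 75% exposure, n = 18) to 27% (four at 30%, n = 20). Between-subject variability is understated: 40% reported against 43% to 69% in the three n = 20 cases. The gaps in the text are certain; the size of the bias is not, because the failure rate, the exposure loss and the 40% CV are assumptions. This should be fixed, although the study has no formal test that it could overturn.

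**What to change.** Replace the adhesion and outlier provisions of PAP 9.1.2, 9.3.3 and 9.3.5 with one rule of one scope:

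- **Main analysis.** PK summaries and the 9.2.3 mixed model include every clinic-day profile for which a patch was applied, whatever the adhesion score. Exclusions are limited to sampling, bioanalytical or no-application reasons. State how a day with a replaced patch is handled.
- **Zero exposure.** Report by visit the number of applications with no quantifiable concentration, since they cannot enter the log-scale model.
- **Sensitivity analyses, labelled as such.** One omits poorly adhering profiles, defined by a fixed cut-off on the Protocol 6.6.4 score (for example 3 or 4) and listed before concentrations are released. The other omits outliers. The cut-off is a choice; measured released dose is a possible alternative, provided it too is fixed in advance.

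The cost is PAP wording and one extra set of tables. No new data are needed, because the adhesion score is already collected. Main-analysis exposure may look lower and its variability higher.
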